4 STUDY PLAN

4.1 Objectives

The purpose of this study is to collect robust data from the Lucid M1 Transcranial Doppler System and NovaGuide System (NovaGuide) devices to validate the Velocity Curvature Index (VCI) as a diagnostic biomarker tool to drive clinical decision making for assessing cerebral vascular occlusions confirmed by standard of care Computed Tomography Angiography (CTA) imaging.

4.1.1 Scope

This study will be conducted with FDA cleared and CE Mark approved product Lucid M1 System, and an investigational device (NovaGuide). The acoustic power delivered by the ultrasound to the patient is only controlled by an FDA / CE Mark cleared product (Lucid M1 System) and the Investigational NovaGuide Robotic System cannot alter the power of the system.

4.2 Study Endpoints

4.2.1 Phase 1 Study Endpoints

Phase 1 Primary Endpoint:

- Area Under the Curve (AUC), Sensitivity, and Specificity of VCI when compared against standard of care CTA imaging for large vessel occlusion assessment.

Phase 1 Secondary Technical Efficacy Endpoint:

- Area Under the Curve (AUC), Sensitivity, and Specificity of a novel machine learning (ML) algorithm when compared against standard of care CTA imaging for large vessel occlusion assessment.
- VCI and experimental ML algorithm compared to prehospital/neurological clinical scales for alternative diagnostic criteria.

Phase 1 Primary Safety Endpoint:

- Incidence of device-related serious adverse events
- Last Known Normal (LKN) to First Hospital Arrival (Initial Door-In) time
- Door to Initial CT imaging (non-contrast) time
- Door to IV-tPA time
- Door to Initial CTA Acquisition time
- Door to Groin Puncture time
- CTA Acquisition to Groin Puncture time

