4.2.2 Phase 2 Study Endpoints

Phase 2 Primary Endpoint:

- Area Under the Curve (AUC), Sensitivity, and Specificity of VCI when compared against standard of care CTA imaging for large vessel occlusion assessment.

Phase 2 Secondary Technical Efficacy Endpoint:

- Area Under the Curve (AUC), Sensitivity, and Specificity of a novel machine learning (ML) algorithm when compared against standard of care CTA imaging for large vessel occlusion assessment.

- VCI and experimental ML algorithm compared to prehospital/neurological clinical scales for alternative diagnostic criteria.

Phase 2 Primary Safety Endpoint:

- Incidence of device-related serious adverse events
- Last Known Normal (LKN) to First Hospital Arrival (Initial Door-In) time
- Door to Initial CT imaging (non-contrast) time
- Door to IV-tPA time
- Door to Initial CTA Acquisition time
- Door to Groin Puncture time
- CTA Acquisition to Groin Puncture time

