4.16.2 Lucid M1 System Scanning Technique (Traditional TCD)

If traditional TCD is conducted using the Lucid M1 System alone, measurements will be collected in the MCA at multiple depths ranges between 45 to 65 mm. The MCA scans will be collected from the trans-temporal window by positioning the probe superior to the zygomatic arch. Once cerebral blood flow velocity (CBFV) of the target vessel is found, the TCD operator will hold this position to record 30 seconds of data.

Cohort A TCD will be subjects identified per CTA findings in the Emergency Room (ER), Stroke Care Unit or Imaging Unit as having a large vessel occlusion. A single TCD scan will be collected by a designated TCD operator using the NovaGuide System or the Lucid M1 System alone (manual TCD). The TCD scan will be collected following CTA within a three (3) hour window and prior to standard of care stroke treatment (e.g., mechanical thrombectomy). Note, tPA can be administered prior to TCD measurements. Study measurements will not delay nor interfere with the patients' standard of care treatment. No follow-up scans will be collected.

Cohort B TCD will be subjects identified per CTA findings in the Emergency Room (ER), Stroke Care Unit or Imaging Unit as having a non-large vessel occlusion. A single TCD scan will be collected by a designated TCD operator using the NovaGuide Robotic System or the Lucid M1 System alone (manual TCD). These scans will be collected within a 24-hour period after enrolment and no follow-up scans will be collected.

Cohort C NO TCD will be subjects identified per CTA findings in the Emergency Room (ER), Stroke Care Unit or Imaging Unit as having a large vessel occlusion. No TCD scans will be conducted and subjects followed through to discharge.

Cohort D NO TCD will be subjects identified per CTA findings in the Emergency Room (ER), Stroke Care Unit or Imaging Unit as having a non-large vessel occlusion. No TCD scans will be conducted and subjects followed through to discharge.

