In this work, we will also measure “Get with the Guidelines, Stroke” metrics from each site and compare them to literature, national and site metrics. This will enable us to demonstrate that the system does not adversely affect standard of care for subjects suspected of stroke. The reason we believe it will not affect standard of care is because the device will be used after initial CT and IV-tPA is administered, while the subject is waiting for CTA or intervention. The time window, although short, is available to allow us to measure both the TCD waveform and CTA to confirm VCI is an effective biomarker. Additionally, the times will be compared against the randomized groups (Cohort C and D).

Door to diagnostic imaging. (Statistical demonstration that show we will not delay anything when adding our NovaGuide workflow to), e.g. “Get with the Guidelines, Stroke”: We will calculate the following for subjects that have NovaGuide measurements:

- IV rt-PA arrive by 2 hour, treat by 3 hour: Percent of acute ischemic stroke patients who arrive at the hospital within 120 minutes (2 hours) of time last known well and for whom IV t-PA was initiated at this hospital within 180 minutes (3 hours) of time last known well.
- % Door to CT \leq 25 minutes: Percent of patients who receive brain imaging within 25 minutes of arrival.
- Door to Puncture (DTP) Time within 90 minutes: (Percentage of patients with acute ischemic stroke who receive mechanical endovascular reperfusion)

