11.2 Phase 2 Statistical Analysis

Primary Endpoint Analysis: Demonstration of VCI biomarker performance at or exceeding 90% ROC-AUC (targeting SEN & SPE greater than 90%) to standard of care imaging across multiple centers.

Here, we will determine the final biomarker performance using the dataset collected and reviewed by the core lab. Similar analyses will be run on the VCI biomarker distributions for the Phase 2 subject group as was done in Phase 1. Additionally, subgroup analyses comparing biomarker results across research sites, and age groups, will be conducted to determine if any age or NovaGuide inter-operator variability effects are present in the data (two-way ANOVA with post-hoc comparisons).

Sample size calculation: In Phase 2, we seek to demonstrate stricter confidence bounds on biomarker diagnostic performance in excess of 90% ROC-AUC. Assuming the biomarker is observed to meet that performance threshold, then a sample of approximately 150 LVO subjects in each patient group is required to attain a one-tailed 95% confidence bound on the observed AUC of 3%. That is, the target AUC and sample size would afford 95% confidence that the underlying general population AUC is greater than 87%. Moreover, across five sites, this results in approximately 30 LVO subjects per site, affording sufficient power for detection of moderate potential inter-site effects in the range of Cohen’s $D \geq 0.75$.

Calculate study and site specific stroke workflow times: Stroke workflow parameters and times are well characterized in literature, including “Get with the Guidelines, Stroke” published by the American Heart Association, Inc. and will be utilized as a historical control comparator for data collected in Phase 2. We will use these published stroke guidelines which have mean times for the stroke workflow parameters to show that we are non-inferior to these when using the NovaGuide device. Additionally, the data will be compared to the corresponding randomized group (Cohort C and D)

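### None of the listed workflow times starts at randomisation, so the randomised check for scan delay rests on intervals partly or wholly fixed beforehand, and transfers may add noise

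*Combined protocol and SAP*

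**What the plan says.** Sections 4.2.1 and 4.2.2 place the same six workflow times under the primary safety endpoint of each phase. The first is "Last Known Normal (LKN) to First Hospital Arrival (Initial Door-In) time". Four are timed from a door (to non-contrast CT, IV-tPA, CTA and groin puncture), and the last is "CTA Acquisition to Groin Puncture time". The list gives "Door to Groin Puncture time" without naming a hospital.

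Section 11.1 adds percentage measures, including "Door to Puncture (DTP) Time within 90 minutes", again with no hospital named. It then gives the randomised comparator: "Additionally, the times will be compared against the randomized groups (Cohort C and D". In section 11.2 the published stroke-guideline times "will be utilized as a historical control comparator for data collected in Phase 2", with an aim of non-inferiority but no margin. The comparison with Cohorts C and D is repeated there.

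Section 4.9 places randomisation after all entry criteria are met and consent is obtained. Those criteria (4.6.1, 4.6.2) include head CT and CTA findings. Balancing factors are site, NIHSS, age, occlusion location and time of day of CT; transfer status is not among them. Section 4.18 collects workflow times as defined by Get With The Guidelines and lists no transfer field.

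**The concern.** A randomised comparison can show the effect of the scan only through what happens after allocation. If an interval ends before allocation, any difference between arms is chance. If it begins well before and ends after, the part before allocation adds variance and no information.

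Several of the listed times are of the first kind and door-to-puncture is of the second. Inter-hospital transfer would make the second problem worse: no entry criterion excludes transferred patients, and the words *first* and *initial* in the arrival item suggest that a later hospital was contemplated. At stake is the claim in 11.1 that the system does not adversely affect standard of care. A noisy measure makes a real delay easier to miss, and a benchmark comparison on a mismatched clock can look worse for reasons unrelated to the device.

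**Working it through.** **1. Which times the scan can affect**

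| Listed time | Position relative to randomisation | Can show a scan delay? |
|---|---|---|
| LKN to first arrival | ends before | no |
| Door to non-contrast CT | ends before (CT is an entry criterion) | no |
| Door to CTA | ends before (CTA defines the cohort) | no |
| Door to IV-tPA | 11.1 expects tPA before device use | little or none |
| Door to puncture | starts before, ends after | yes, diluted |
| CTA to puncture | starts before, ends after; uses no door | yes, less diluted unless the CTA was done elsewhere |

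**2. The plan's own figures.** The protocol states no SD, margin, power or sample size for any workflow time, so there is nothing to reproduce on this point. The arm sizes come from AUC precision. Those figures do reproduce: the one-sided 95% bound is 0.064 at AUC 0.85 with 50 per group (stated: under 7%) and 0.030 at AUC 0.90 with 150 per group (stated: 3%).

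**3. Inputs for the transfer effect**
- From the synopsis: 54 LVO subjects per arm in Phase 1 and 156 in Phase 2. Section 4.4 gives only 312 subjects for Phase 2 and does not mention a No TCD group there.
- Assumed, because the documents give none of them: direct door-to-puncture log-normal with median 100 minutes and log-SD 0.4; transfer adding T = 120 minutes on average (SD 40); transfer share p from 0 to 35%; true delay 20 minutes; one-sided 5% test of means, unadjusted; every subject punctured.

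**4. Formulas.** Direct mean = 100 × exp(0.08) = 108 minutes. Direct SD s = 108.3 × √(exp(0.16) − 1) = 45 minutes. On a first-hospital clock, the mean shift is p × T and the variance is s² + p × 40² + p(1 − p) × 120². Power ≈ Φ(20 / (SD × √(2/n)) − 1.645).

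**5. Results**
- p = 0: SD 45. At n = 54, SE = 45.1 × 0.1925 = 8.7 and power ≈ Φ(0.66) = 75%.
- p = 10%: variance 2034 + 160 + 1296 = 3490, SD 59, SE 11.4, power ≈ Φ(0.11) = 54%. Mean shift 0.10 × 120 = 12 minutes.
- p = 35%: variance 2034 + 560 + 3276 = 5870, SD 77, SE 14.7, power ≈ Φ(−0.29), about 38%. Mean shift 0.35 × 120 = 42 minutes (108 to 150).

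A simulation with 4,000 replicates per case gives the same values: 75%, 54% and 38%. At 156 per arm it gives 99%, 90% and 76%. The share punctured within 90 minutes falls from 40% to 36% and 26%.

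**6. Sensitivity.** Adjusting for transfer status on the same first-hospital data gives power at 54 per arm of 71% (10% transfers) and 64% (35%), and at 156 per arm 98% and 97%. Log-scale analysis at 54 per arm gives 87%, 72% and 52% for 0, 10% and 35% transfers. A separate closed-form check with a direct SD of 40, transfer SD 45 and 25% transfers gives a 30-minute mean shift (0.25 × 120), three times the variance, and a 95% half-width for A versus C rising from 15.1 to 26.2 minutes at 54 per arm.

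**The case against.** The strongest reply is that this is missing detail rather than error. Section 4.18 defers workflow definitions to Get With The Guidelines, which may settle the door; that source is not available here, so its silence cannot be claimed. No transfer rate is given, and recruiting from a Stroke Care Unit ("Cohort A TCD will be subjects identified per CTA findings in the Emergency Room (ER), Stroke Care Unit or Imaging Unit") does not show inter-hospital transfer. Most of the computed power loss comes from an unadjusted test that the plan never specifies. CTA-to-puncture is already listed and needs no door, and the three-hour scan window in 4.16.2 may limit how much transfer time it can carry. All of this stands, and it keeps the transfer figures conditional.

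A reader might also infer that the protocol defines two conflicting doors, the first hospital in 4.2 and the treating hospital in 11.1. The text does not support that. The first-hospital wording ends the LKN interval. The phrase in 11.1, "for whom IV t-PA was initiated at this hospital within 180 minutes (3 hours) of time last known well", says where tPA was started, in a percentage timed from last known well. Neither door-to-puncture item names a hospital. The tPA percentage and the door-to-tPA duration are different measures, not one measure on two clocks.

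One passage cuts the other way on timing: 11.1 describes the device being used while the subject waits for CTA or intervention. Sections 4.9 and 4.16.2 place randomisation and the Cohort A scan after CTA, so these passages need reconciling.

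What the reply does not answer is the choice of interval. Even with no transfers and a perfectly defined door, no listed time begins where the arms begin to differ.

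**Conclusion.** The point holds as a weakness in the choice of delay measure. Times to arrival, CT and CTA are settled before randomisation and say nothing about the scan. Door-to-puncture contains pre-randomisation time, and CTA-to-puncture contains less of it unless the CTA was done at another hospital. That part follows from the documents and needs no assumption.

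The size of the transfer effect is wholly assumed: at 54 per arm, unadjusted power falls from about 75% to 54% at 10% transfers and 38% at 35%. The loss is much smaller after adjustment for transfer status, and with no transfers there is none. Because arrival and transfer normally precede allocation, the randomised contrast is not biased in expectation; it only loses precision. The comparison with published times does shift, by roughly transfer share × transfer time, if the clocks differ.

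It would go too far to say that the choice of door could reverse a pass or fail against the benchmark. No pass mark is set for the 90-minute percentage and no non-inferiority margin is given, so there is no decision rule to reverse.

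**What to change.** - In 4.2.1, 4.2.2, 11.1 and 11.2, make minutes from randomisation to groin puncture, among punctured subjects, the main delay measure for Cohort A versus Cohort C. The IVRS/IWRS issues the assignment, so its time should be available, and puncture time is already needed for the listed endpoints. Report the number punctured in each arm beside it.
- Keep the door-based times for the benchmark comparison only. State in the protocol which hospital's door applies, using the same definition as the benchmark.
- Record transfer status, so that transferred subjects can be reported separately.

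The cost is wording in four sections and one CRF field; no procedure or subject is added. The small downside is that the randomised measure cannot be set directly against published door-to-puncture figures, which is why the door-based times stay for that purpose.

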4.2.2 Phase 2 Study Endpoints

Phase 2 Primary Endpoint:

- Area Under the Curve (AUC), Sensitivity, and Specificity of VCI when compared against standard of care CTA imaging for large vessel occlusion assessment.

Phase 2 Secondary Technical Efficacy Endpoint:

- Area Under the Curve (AUC), Sensitivity, and Specificity of a novel machine learning (ML) algorithm when compared against standard of care CTA imaging for large vessel occlusion assessment.

- VCI and experimental ML algorithm compared to prehospital/neurological clinical scales for alternative diagnostic criteria.

Phase 2 Primary Safety Endpoint:

- Incidence of device-related serious adverse events
- Last Known Normal (LKN) to First Hospital Arrival (Initial Door-In) time
- Door to Initial CT imaging (non-contrast) time
- Door to IV-tPA time
- Door to Initial CTA Acquisition time
- Door to Groin Puncture time
- CTA Acquisition to Groin Puncture time

4.3 Study Design

This study is a multi-center, multi-Phase, multi-cohort, prospective, randomized, open, blinded endpoint (PROBE), non-significant risk (NSR) device study including up to 420 evaluable subjects measured with the study device(s).

4.4 Study Population Size

Phase 1: Approximately 108 subjects will be randomized to the TCD only group (54 subjects in Cohort A and 54 subjects in Cohort B). An additional 108 subjects will be randomized to the NO TCD group. An interim feasibility and safety assessment will be completed after Phase 1.

Phase 2: Approximately 312 subjects presenting with stroke like symptoms for which diagnostic imaging has been ordered will be enrolled (156 in Cohort A and 156 in Cohort B). Primary and secondary endpoints will be calculated after completion of Phase 2.

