1 PROTOCOL SYNOPSIS

Protocol Synopsis:	
Study Sponsor: NovaSignal Corp. [name] National Institute of Health (NIH)	Protocol No.: NA-01STR-03 Regulatory Class: II Study Device(s): NovaGuide and/or Lucid TCD System Development Phase: Phase 1: Feasibility; Phase 2: Pivotal
Study Title: Evaluate a NeXt Generation Portable Diagnostic Platform for Determination and Immediate Triage of Emergency Large Vessel Stroke (EXPEDITE IIA)	
Overall Study Design: This study is a multi-center, multi-phase, multi-cohort, prospective, randomized, open, blinded endpoint (PROBE), non-significant risk (NSR) device study including up to 420 evaluable subjects measured with the study device(s).	
Objective: The purpose of this study is to collect robust data from the robotic NovaGuide device or the Lucid TCD device to validate the Velocity Curvature Index (VCI) as a diagnostic biomarker tool to drive clinical decision making for assessing cerebral vascular occlusions confirmed by standard of care Computed Tomography Angiography (CTA) imaging.	
Number of Subjects: Phase 1: Up to 216 (54 Cohort A TCD, 54 Cohort A No TCD) (54 Cohort B TCD, 54 Cohort B No TCD) Phase 2: Up to 624 (156 Cohort A TCD, 156 Cohort A No TCD) (156 Cohort B TCD, 156 Cohort B No TCD)	Number of Sites: Phase 1: Up to 3 sites Phase 2: Up to 5 sites
Duration of Study Participation: 
Phase 1 Enrollment: 18 monthsPhase 2 Enrollment: 24 monthsTotal Study Duration: 1 to 7 days	
Phase 1 Study Design	
Phase 1 will include up to 54 subjects enrolled in Cohort A and 54 subjects enrolled in Cohort B. An interim feasibility and safety assessment will be completed after Phase 1.	
Phase 1 and Phase 2 Entry Criteria:	
Cohort A LVO	
Inclusion Criteria	

Subject aged 18 years and olderLarge vessel occlusion of the intracranial ICA, MCA (M1, M2), or multiple areas of the aforementioned locations confirmed by computed tomography angiography (CTA)Subject or Legally Authorized Representative has the ability to provide informed consent and comply with the protocol.	
Exclusion Criteria	

Head CT findings consistent with acute primary intracranial hemorrhage (SAH, ICH, etc.)Hemodynamically unstable patients requiring pharmacological support for hypertension	

Protocol Synopsis:	

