Study Sponsor: NovaSignal Corp. [name] National Institute of Health (NIH)	Protocol No.: NA-01STR-03 Regulatory Class: II Study Device(s): NovaGuide and/or Lucid TCD System Development Phase: Phase 1: Feasibility; Phase 2: Pivotal
3. Subjects who underwent partial or full craniotomy 4. Additional intracranial pathologies present (tumor, hydrocephalus, etc.) 5. Anticipated insufficient time to acquire a complete initial TCD scan as described by the protocol 6. Subjects who have a physical limitation preventing placement of the system.	
Cohort B Non-LVO	
Inclusion Criteria	
1. Subject aged 18 years and older 2. Non-large vessel occlusion confirmed by computed tomography angiography (CTA) 3. Subject or Legally Authorized Representative has the ability to provide informed consent and comply with the protocol.	
Exclusion Criteria	
1. CTA findings including: a. Occlusions in the common carotid artery, internal carotid artery, anterior carotid artery, middle cerebral artery (M1 and M2 segments), anterior communicating artery, basilar artery, posterior communicating artery and vertebral arteries. 2. Head CT findings consistent with acute primary intracranial hemorrhage (SAH, ICH, etc.) 3. Hemodynamically unstable patients requiring pharmacological support for hypertension 4. Subjects who underwent partial or full craniotomy 5. Anticipated insufficient time to acquire a complete set of scans as described by the protocol 6. Subjects who have a physical limitation preventing placement of the system.	
Phase 2 Study Design	
Phase 2 will include up to 312 subjects (156 cohort A and 156 in cohort B) presenting with stroke like symptoms for which diagnostic imaging has been ordered. Primary and secondary endpoints will be calculated after completion of Phase 2.	

Protocol Synopsis:	
Study Sponsor: NovaSignal Corp. [name] National Institute of Health (NIH)	Protocol No.: NA-01STR-03
	Regulatory Class: II
	Study Device(s): NovaGuide and/or Lucid TCD System
	Development Phase: Phase 1: Feasibility; Phase 2: Pivotal
Imaging Core Lab Analysis: All imaging data will be sent to a core laboratory which will provide independent quantitative and qualitative assessment of all study data. They will be blinded to the study and radiology report data and provide independent review.	

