4.8 Informed Consent and Screening

Subject identification and eligibility will be determined by the PI or study team based on their clinical assessment of the potential subject while that patient is undergoing standard of care for their neurological condition.

Before participation in the study, candidates who may be eligible for the study will be provided with an informed consent according to 21 CFR 56 and 45 CFR 160-164 and guidelines of the Investigational Review Board of the institution at which the study is being conducted. Candidates will be given time to review the consent form and ask questions about the study. The investigator will obtain written informed consent from the candidate. The candidate or legal representative must sign the consent form prior to enrolment. Candidates will also be required to sign a Health Insurance Portability and Accountability Act (HIPAA) form which includes a Privacy Rule. This rule gives special safeguards to Protected Health Information (PHI) that is identifiable or can be directly linked to the subject (e.g., social security number, name, birth date). This authorization may be part of the informed consent form or separate. If applicable to the investigator site location, candidates will also be required to sign the California Experimental Subject Bill of Rights.

A subject will be considered enrolled at the time of Informed Consent signature.

Potential subjects and/or their legal authorized representative / surrogate will be guided through the informed consent process by a member of the research team. This process includes informing the subject of the study procedures (in simple language), answering all questions, and obtaining written consent (Consent Form). The investigator or delegated study staff is responsible for obtaining written informed consent from each potential study participant. Informed consent should be obtained, when required, in written format and using a form approved by the local IRB. The subject must receive a copy of the signed and dated informed consent. Waivers of consent will not be utilized in this study.

A subject will be considered enrolled at the time of Informed Consent signature.

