4.9 Randomization

Randomization will occur once subject has satisfied all inclusion/exclusion criteria and informed consent has been obtained. Subjects will be randomly assigned in equal number (1:1) to one of two procedure arms within each cohort: 1) TCD Exam or 2) No TCD Exam. The number of procedures and controls will be balanced within investigational sites, by baseline NIHSS severity (≤ 17 versus >17), age (<70 years versus ≥ 70 years at the time of randomization) occlusion location (M1 versus all other), and time of day of initial CT scan (0900-1700 and 1701-0859). Subject allocation to procedure will be accomplished by using an interactive web response (IWRS) or interactive voice response system (IVRS).

At the time of randomization, the site will access IVRS/IWRS and enter subject's screening NIHSS, age, occlusion location, and time of CT scan. Based on the information provided, the system will automatically generate the assigned treatment. If the site is unable to access website for randomization, an interactive voice response randomization is also available by phone.

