4.10 Numbering of Study Subjects

Each site will be assigned a site number at the beginning of the study and each enrolled subject will be assigned a subject number. Subjects will be considered enrolled in the screening phase

when the informed consent has been signed and enrolled in the randomized phase when the randomization system (IVRS/IWRS) provides a treatment assignment. Site study coordinators will assign/obtain the subject number from the IVRS/IWRS and document the subject number on the screening/enrollment log once the subject has signed the informed consent. The subject number will consist of the study number and the site number followed by a sequential number that begins with "001". Site will also need to access the IVRS/IWRS to register the subject in the screening phase (detailed instructions on accessing the IVRS/IWRS will be provided in the user manual developed by the IVRS/IWRS vendor).

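### Phase 2 enrolment is given as 312 in section 4.4 and the synopsis design text but as up to 624 in the synopsis count; 312 fits only the scanned subjects

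*Combined protocol and SAP*

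**What the plan says.** The Phase 2 size appears in three places.

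- Section 4.4: "Approximately 312 subjects presenting with stroke like symptoms for which diagnostic imaging has been ordered will be enrolled", split as 156 in Cohort A and 156 in Cohort B.
- Synopsis, Phase 2 Study Design: "Phase 2 will include up to 312 subjects (156 cohort A and 156 in cohort B").
- Synopsis, Number of Subjects: "Phase 2: Up to 624 (156 Cohort A TCD, 156 Cohort A No TCD"), with the same two cells for Cohort B.

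For Phase 1, section 4.4 gives 108 subjects randomised to TCD (54 per cohort) and then adds: "An additional 108 subjects will be randomized to the NO TCD group". Its Phase 2 line has no such sentence. The synopsis Phase 1 paragraph leaves out the No TCD group as well: "Phase 1 will include up to 54 subjects enrolled in Cohort A and 54 subjects enrolled in Cohort B", although the Number of Subjects row gives up to 216.

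On allocation, section 4.9 says: "Subjects will be randomly assigned in equal number (1:1) to one of two procedure arms within each cohort". It does not limit this to Phase 1.

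Enrolment is defined twice. Section 4.8 says: "A subject will be considered enrolled at the time of Informed Consent signature". Section 4.10 separates a screening phase, entered at consent, from subjects "enrolled in the randomized phase when the randomization system (IVRS/IWRS) provides a treatment assignment".

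**The concern.** Both definitions of enrolment count subjects in both arms, because consent comes before randomisation and treatment assignment is the randomisation itself. A Phase 2 enrolment of 312 therefore includes the No TCD subjects, and half of those randomised would never be scanned. The primary endpoint, the AUC of VCI against CTA, can use scanned subjects only.

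Section 4.4 is where a site, an IRB or the randomisation vendor would look for the target, and section 4.5 makes the study complete once all subjects are enrolled and all data collected. Someone working to 312 would stop at half of the synopsis count. The precision claimed in section 11.2 and the scanned total in section 4.3 would then be missed. Section 4.4 also leaves the size of the Phase 2 No TCD group unstated, and that group is the randomised comparator for the workflow times listed among the primary safety endpoints.

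**Working it through.** **Inputs**

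- Cell sizes: 54 (Phase 1) and 156 (Phase 2) per cohort and arm (synopsis, Number of Subjects).
- Allocation 1:1 within cohort (4.9).
- Up to 420 evaluable subjects scanned over both phases (4.3).
- About 150 per group for a one-sided 95% bound of 3% at AUC 0.90, lower limit 87% (11.2).
- About 30 LVO subjects per site at five sites, to detect inter-site effects of d ≥ 0.75 (11.2).

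**Step 1: which count is which**

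- All four cells: 4 × 54 = 216 and 4 × 156 = 624. These are the synopsis totals.
- TCD cells only: 2 × 54 = 108 and 2 × 156 = 312.
- Scanned over both phases: 108 + 312 = 420, exactly the figure in 4.3.

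So 420 is reached only if all 312 are scanned. With 312 as the total randomised, 312 / 2 = 156 are scanned, or 78 per cohort, and the two-phase scanned total is 108 + 156 = 264. If 312 is counted at consent (4.8), 78 is an upper limit, since section 4.11 allows screen failures.

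**Step 2: does Phase 2 have a No TCD group?** Yes. The schedule in 4.15 covers both phases and includes Cohorts C and D, and 11.2 compares Phase 2 data with those cohorts.

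**Step 3: the precision claim.** The protocol names no variance method for the AUC. Assume Hanley-McNeil with n per group:

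Var = [A(1−A) + (n−1)(Q1−A²) + (n−1)(Q2−A²)] / n², with Q1 = A/(2−A) and Q2 = 2A²/(1+A).

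At A = 0.90, Q1 = 0.8182, Q2 = 0.8526 and A² = 0.81, so Q1−A² = 0.0082 and Q2−A² = 0.0426. The bound is 1.645 × SE.

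| n per group | SE | Bound | Lower limit |
|---|---|---|---|
| 150 (11.2) | 0.0185 | 0.0304 | 0.870 |
| 156 (synopsis cell) | 0.0181 | 0.0298 | 0.870 |
| 78 (312 as total) | 0.0256 | 0.0422 | 0.858 |

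The first two rows reproduce the plan's 3% and 87%. The third does not.

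**Step 4: sensitivity to the formula.** At n = 78, the exact equal-variance binormal variance gives 4.0 points and the Obuchowski binormal formula 4.9, so the lower limit runs from 86.0% down to 85.1%. The Obuchowski formula gives 3.5 points even at n = 150, so part of its 4.9 comes from the formula and not from halving the sample. The Hanley-McNeil figure is the one that matches the plan's own 3%.

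**Step 5: inter-site power.** For d = 0.75 between two sites (normal approximation, two-sided alpha of 0.05 assumed), power is 83% with 30 per site. With 78 over five sites, 15 to 16 per site, it is 54% to 56%.

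**Step 6: Phase 1.** Section 4.4 is sound. With 54 per cohort at AUC 0.85 the bound is 6.2 points and the lower limit 78.8%, above the 78% benchmark in 11.1. Only the synopsis Phase 1 paragraph, read literally, would give 27 scanned per cohort: 8.8 points, lower limit 76.2%.

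**The case against.** The strongest reply is that nothing is miscalculated and the design can be recovered. Both 312 and 624 follow exactly from the cell sizes. The synopsis count lists the four cells, 4.3 gives 420 scanned, 4.9 gives the ratio, 11.2 gives the group size, and the Phase 1 line of 4.4 shows the intended structure. A reader would have to ignore all of these to stop at 312 enrolled, so the loss of precision describes a misreading and not the plan. That stands, and it is why this is a correction to the text and not a finding of an underpowered design. It does not remove the conflict. The section that defines the population size gives a total that disagrees with the synopsis, and because the No TCD group is named there for Phase 1 only, a reader could infer that Phase 2 has none.

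Three narrower points also stand.

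- The literal Phase 1 reading is already excluded by section 4.4 and by the synopsis count of 216, so its figures carry little weight.
- The cohort labels are mixed and do not split cleanly by section. Sections 4.6 and 4.9 use A and B for all LVO and non-LVO subjects. Section 4.16.2 uses A and B for the TCD groups and C and D for the No TCD groups. The schedule in 4.15 has columns A to D, but its footnote refers to a No TCD group in either cohort.
- The 420 in 4.3 are evaluable subjects, which is not quite the same as all subjects randomised to TCD.

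**Conclusion.** The concern holds. As a Phase 2 enrolment total, 312 in section 4.4 and the synopsis design text is wrong by a factor of two against the synopsis count. It is the number to be scanned, and the matching total is 624. Over both phases this gives 216 + 624 = 840 enrolled and 420 scanned.

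If 312 were applied as the total, at most 78 per cohort and 264 overall would be scanned. The AUC bound would widen from 3.0 to 4.2 points, and the lower limit would fall from 87% to 85.8%. These precision figures assume an observed AUC of 0.90 and the Hanley-McNeil variance, which is not named in the protocol but reproduces its 3%. The counts themselves need no assumption beyond the 1:1 ratio and, for 264, 108 scanned in Phase 1. The text should be corrected, and the confidence in this is high.

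**What to change.** Ask the sponsor to confirm that 624 is the intended Phase 2 total. Then:

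- In section 4.4 and the synopsis Phase 2 paragraph, state that about 312 subjects are randomised to TCD (156 LVO, 156 non-LVO) and a further 312 to No TCD, 624 in total.
- In the synopsis Phase 1 paragraph, state 108 TCD plus 108 No TCD, 216 in total.
- Use one labelling throughout: either Cohorts A and B, each with a TCD and a No TCD arm, or Cohorts A to D.
- Say whether each count refers to consented, randomised or evaluable subjects.

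If 624 is confirmed, the cost is wording only, and the size in the synopsis count does not change. If the sponsor instead means 312 in total, then the 624, the 420 in section 4.3 and the precision statement in section 11.2 must all be revised.
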